### 16.2 Primary Efficacy

To evaluate the equivalence in efficacy between AGA BETA BS and Fabrazyme® after 6 Months of treatment in patients with Fabry disease previously stabilized with Fabrazyme®, by measuring disease biomarker.

**The primary efficacy variable is**

#### 16.2.1 Intercurrent Event Handling and Data Imputation for Primary Efficacy Variable(s)

Not Applicable

---

Document: \\needc-vnasc01\Biosdata\Biosidus\Agalsidase Beta\YZAA1358\Biostatistics\Documentation\SAP

Author: [name]

Version Number: V1.0

Version Date: 08May2025

Template No.: CS\_TP\_BS016 Revision 7

Reference: CS\_WI\_BS005

Effective Date: 01Nov2021

## 16.2.2 Primary Analysis of Primary Efficacy Variable(s)

The primary analysis of the primary efficacy variable will be performed based on both ITT population and PP populations.

The primary efficacy analysis will aim to demonstrate the equivalence in efficacy based on the mean serum Lyso-Gb3 marker ratio after 26 weeks of treatment, considering Serum level of the marker Lyso-Gb3 after 26 weeks divided by plasma level of the marker Lyso-Gb3 at baseline

The primary objective of this study is to test the hypothesis that:

H0: Ratio of serum level of Lyso-Gb3 marker at week 26 and serum level of the marker LysoGb3 at baseline is less than 80% or greater than 125%. This means that there is a difference between AGA BETA BS (Test) and Fabrazyme® (Reference) after 6 months.

H1: Ratio of serum level of Lyso-Gb3 marker at week 26 and serum level of the marker Lyso-Gb3 at baseline is in between 80% and 125%. This means that there is no difference between AGA BETA BS (Test) and Fabrazyme® (Reference) after 6 months.

Mathematically,

H0:  $(\mu_T / \mu_R) \leq 0.80$  or  $(\mu_T / \mu_R) \geq 1.25$

H1:  $0.80 < (\mu_T / \mu_R) < 1.25$

where  $\mu_T / \mu_R$  represent the ratio of means of plasma level of Lyso-Gb3 marker at week 26 and mean of plasma level of the marker LysoGb3 at baseline indicating a difference between AGA BETA BS (Test) and Fabrazyme® (Reference)

A paired t-test will be fit to the log-transformed mean of Lyso-GB3 Marker Baseline value and Lyso-GB3 Marker after 26 weeks of treatment . Equivalence will be declared if the 95% CI for the postbaseline and baseline ratio of plasma level of the marker LysoGb3 is entirely contained within the prespecified equivalence margin of 80% to 125% for the ITT population.

Mean change from baseline of plasma Lyso-Gb3 after 26 weeks of treatment will be calculated and a 95% CI for the difference will be computed. The mean change from baseline and its CI will be exponentiated to obtain the ratio of the means between after 26 weeks of treatment and baseline and its 95% CI. Equivalence will be determined if the 95%CI for the postbaseline and baseline ratio lies completely within the range 0.80 to 1.25 for the ITT population.

Analysis will be performed based on both ITT population and PP population. Descriptive statistics will be presented for the actual and change from baseline data for phenotype wise (classic Fabry males, later onset Fabry males, and Fabry females) and overall, for ITT and PP population.

Patient Profile for Lyso-GB3 Marker by Visit and Lyso-GB3 Marker (Week 26 and Week 54) will be presented as a figure.

Document: \\needc-vnasc01\Biosdata\Biosidus\Agalsidase Beta\YZAA1358\Biostatistics\Documentation\SAP

Author: [name]

Version Number: V1.0

Version Date: 08May2025

Template No.: CS\_TP\_BS016 Revision 7

Reference: CS\_WI\_BS005

Effective Date: 01Nov2021

## 16.3 Secondary Efficacy

The secondary efficacy analyses will be performed for the ITT population and PP population.

### 16.3.1 Analysis of Secondary Efficacy Endpoints

- Mean serum Lyso-Gb3 marker ratio after 54 weeks of treatment will be analyzed in an analogous way to the primary endpoint. No equivalence testing will be performed. Additionally, p-value will be presented for secondary efficacy analysis. Analysis will be based on both ITT population and PP Population.
- Pain severity and impact of pain on daily functions will be assessed through BPI Questionnaire based on the methods provided in [Appendix 3 \(BPI\)](#). Endpoint will be evaluated for average scores, across each of the domain item (Pain severity and Pain interference items) and descriptive statistics will be presented using actual and change from baseline after 26 weeks and 54 weeks of treatment for ITT Population.
- The change in health perception before and after treatment with AGA BETA BS in participants with FD previously stabilized with Fabrazyme® will be measured by the Rand -36. Descriptive statistics will be presented using actual and change from baseline data for Rand -36 scores at week 26 and week 54 for ITT Population. Additionally, Scores will be classified into different domain items namely physical functioning, Bodily Pain, general health, vitality, social functioning, role physical, Role Emotional and Mental health based on methods provided in [appendix \(Rand-36\)](#).

## 16.4 Exploratory Efficacy

Not Applicable.

## 17 SAFETY OUTCOMES

All outputs for safety outcomes will be based on the SAF population or ITT population. For Safety variables, formal statistical comparisons between treatment groups will not be performed.

---

Document: \\needc-vnasc01\Biosdata\Biosidus\Agalsidase Beta\YZAA1358\Biostatistics\Documentation\SAP

Author: [name]

Version Number: V1.0

Version Date: 08May2025

Template No.: CS\_TP\_BS016 Revision 7

Reference: CS\_WI\_BS005

Effective Date: 01Nov2021

## 17.1 Adverse Events

All Adverse Events (AE) recorded in study will be coded using the MedDRA central coding dictionary version 25.1.

An AE will be defined as a treatment-emergent adverse event (TEAE) if they start on or after the date of the first dose of AGA BETA BS and would be counted only under treatment period and Non-TEAEs under Lead-in period in treatment period.

See [Appendix 1](#) for handling of partial dates for AEs. In the case where it is not possible to define an AE as treatment emergent or not, the AE will be classified by the worst case, i.e. treatment emergent.

Adverse events collected during the trial will be summarized by treatment groups and Period based on SAF population. Adverse events Listings will be presented for ITT population.

The number of AE and the number and percentage of patients experiencing AE will be summarized by severity and relationship to the Fabrazyme® and AGA BETA BS.

SAEs and AEs leading to premature study discontinuation will be summarized.

Listings will be provided for AEs based on severity and relationship to study medication.

Listings will be provided for AEs, SAE and AEs leading to discontinuation from study.

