#### **6.8.2 Rescue Medicine**

There is no rescue medication planned for this study.

If the participant is presenting a failure of expected pharmacological action and the disease progression or signs or symptoms of disease progression are more severe than expected for the participant's condition under treatment, will be left to the Investigator's discretion whether the participant should be discontinued from the clinical trial and go back to his or her former treatment.

In the presence of clinically significant changes or biochemical modifications of the Lyso-Gb3 biomarker, each investigator must distinguish if the observed changes are still related to the natural history of disease or to an eventual lack of efficacy. In such case, the investigator will decide whether it is pertinent to withdraw the patient from the study

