### **7.1 Discontinuation of Study Intervention**

It may be necessary for a participant to permanently discontinue study intervention. If study intervention is permanently discontinued, the participant will remain in the study but instead of following the sequential procedures established in the SoA, he/she will only receive telephone follow-up, if he/she agrees, at the same planned timepoints to evaluate his or her general condition. See the SoA in Section [1.3](#) for data to be collected at the time of discontinuation of study intervention and follow-up and for any further evaluations that need to be completed.

Participants will discontinue study intervention if any of the following occur:

- Eligibility criteria violation was noted after the participant started study treatment. In that case, the Sponsor, or Sponsor designee, must be contacted. An exception may be granted in rare circumstances for which there is a compelling safety reason to allow the participant to continue with study intervention. In these rare cases, the Investigator must obtain documented approval from the Sponsor, or Sponsor designee, to allow the participant to continue with study intervention.
- Participant is significantly noncompliant with study procedures which would put the participant at risk for continued participation in the study.
- Any AE, laboratory abnormality, or intercurrent illness which, in the judgment of the Investigator, presents a substantial clinical risk to the participant with continued study treatment.
- Clinically significant changes or biochemical modifications of the Lyso-Gb3 biomarker, that, at the Investigator's discretion, represent a lack of efficacy of the investigational product.

Participants who discontinue study intervention might be replaced.

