#### **8.4.1 Time Period and Frequency for Collecting Adverse Events and Serious Adverse Event Information**

All AEs and SAEs will be collected from the signing of the ICF until the last visit, at the time points specified in the SoA (Section [1.3](#)).

The participant will receive a diary to record any AE that may occur during the study. The delivery of the diary to the participant and its collection for evaluation is described in the SoA (Section [1.3](#)). The participant must be instructed to take the diary with them to each medical

visit and each infusion appointment for evaluation. All information collected in the diary must be recorded on the eCRF.

Medical occurrences that begin before the start of study intervention but after obtaining informed consent will be recorded as medical history/current medical conditions, not as AEs.

All SAEs will be recorded and reported to the Sponsor or designee immediately and under no circumstance should this exceed 24 hours of the Investigator's awareness of the event, as indicated in Section 10.5. The Investigator will submit any updated SAE data to the Sponsor or designee within 24 hours of their awareness of the updated information.

Investigators are not obligated to actively seek information on AEs or SAEs after conclusion of the study participation. However, if the Investigator learns of any SAE, including a death, at any time after a participant has been discharged from the study, and he/she considers the event/cause of death to be reasonably related to the study intervention or study participation, the Investigator must promptly notify the Sponsor or designee.

The method of recording, evaluating, and assessing causality of AE and SAE and the procedures for completing and transmitting safety reports are provided in Section 10.5.

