## APPENDIX 2. PARTIAL DATE CONVENTIONS

**Imputed dates will NOT be presented in the listings.**

### Algorithm for Treatment Emergence of Adverse Events:

START DATE	STOP DATE	ACTION
Known	Known/Partial/ Missing	If start date < study med start date, then not TEAE. If start date >= study med start date, then TEAE
Partial, but known components show that it cannot be on or after study med start date	Known/Partial/ Missing	Not TEAE
Partial, could be on or after study med start date OR Missing	Known	If stop date < study med start date, then not TEAE. If stop date >= study med start date, then TEAE

Document: \\needc-vnasc01\Biosdata\Biosidus\Agalsidase Beta\YZAA1358\Biostatistics\Documentation\SAP

Author: [name]

Version Number: V1.0

Version Date: 08May2025

Template No.: CS\_TP\_BS016 Revision 7

Reference: CS\_WI\_BS005

Effective Date: 01Nov2021

START DATE	STOP DATE	ACTION
	Partial	Impute stop date as latest possible date (i.e. last day of month if day unknown or 31st December if day and month are unknown), then: If stop date < study med start date, then not TEAE. If stop date >= study med start date, then TEAE
	Missing	Assumed TEAE

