### Algorithm for Prior / Concomitant Medications:

START DATE	STOP DATE	ACTION
Known	Known	If stop date < study med start date, assign as prior If stop date >= study med start date and start date <= study med end date, assign as concomitant If stop date >= study med start date and start date > study med end date, assign as post study
	Partial	Impute stop date as latest possible date (i.e. last day of month if day unknown or 31st December if day and month are unknown), then: If stop date < study med start date, assign as prior If stop date >= study med start date and start date <= study med end date, assign as concomitant If stop date >= study med start date and start date > study med end date, assign as post treatment
	Missing	If stop date is missing could never be assumed a prior medication If start date <= study med end date, assign as concomitant If start date > study med end date, assign as post treatment

Document: \\needc-vnasc01\Biosdata\Biosidus\Agalsidase Beta\YZAA1358\Biostatistics\Documentation\SAP

Author: [name]

Version Number: V1.0

Version Date: 08May2025

Template No.: CS\_TP\_BS016 Revision 7

Reference: CS\_WI\_BS005

Effective Date: 01Nov2021

START DATE	STOP DATE	ACTION
Partial	Known	Impute start date as earliest possible date (i.e. first day of month if day unknown or 1st January if day and month are unknown), then: If stop date < study med start date, assign as prior. If stop date >= study med start date and start date <= study med end date, assign as concomitant If stop date >= study med start date and start date > study med end date, assign as post treatment
	Partial	Impute start date as earliest possible date (i.e. first day of month if day unknown or 1st January if day and month are unknown) and impute stop date as latest possible date (i.e. last day of month if day unknown or 31st December if day and month are unknown), then: If stop date < study med start date, assign as prior. If stop date >= study med start date and start date <= study med end date, assign as concomitant If stop date >= study med start date and start date > study med end date, assign as post treatment
	Missing	Impute start date as earliest possible date (i.e. first day of month if day unknown or 1st January if day and month are unknown), then: If stop date is missing could never be assumed a prior medication If start date <= study med end date, assign as concomitant If start date > study med end date, assign as post treatment

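### The SAP's TEAE rule has a start but no end, so AEs recorded after a participant has stopped AGA BETA BS still count under AGA BETA BS

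*SAP*

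**What the plan says.** - **SAP 17.1** treats AEs as treatment-emergent "if they start on or after the date of the first dose of AGA BETA BS and would be counted only under treatment period".
- **SAP Appendix 2**, treatment-emergence algorithm, applies the same one-sided test when the start date is known: "If start date < study med start date, then not TEAE. If start date >= study med start date, then TEAE". The study-medication end date is not used anywhere in this algorithm.
- **SAP Appendix 2**, medication algorithm, does use that end date. With both dates known: "If stop date >= study med start date and start date > study med end date, assign as post study". With a partial stop date: "If stop date >= study med start date and start date > study med end date, assign as post treatment".
- **SAP Appendix 1** (presentation of treatment groups and periods) provides two groups only: the lead-in period, labelled Fabrazyme, and the treatment period, labelled AGA BETA BS.
- **Protocol 7.1**: "If study intervention is permanently discontinued, the participant will remain in the study". Follow-up is then by telephone only, if the participant agrees, at the remaining planned timepoints.
- **Protocol 8.4.1**: "All AEs and SAEs will be collected from the signing of the ICF until the last visit". The sentence goes on to tie collection to the schedule of activities.
- **Protocol 6.8.2** lets the investigator decide whether a participant with treatment failure should leave the trial and "go back to his or her former treatment".

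**The concern.** The safety objective is to characterise AGA BETA BS. Under the rule as written, once a participant has had one dose, every later recorded AE belongs to AGA BETA BS for as long as the participant stays in the study, whatever is being infused by then. The protocol deliberately keeps people in the study after they stop the drug, so off-drug time can exist by design.

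Those affected are the early stoppers, whose safety data will be read most closely. With about 20 participants, one person moves any incidence row by 1/20 = 5 percentage points. The medication rules in the same appendix do separate out what starts after treatment, so the gap is specific to AEs.

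**Working it through.** The plan gives no figure for this point. The check is a trace of the rule plus date arithmetic.

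**Inputs.** There are 27 infusions every 14 days (protocol 4.1), the first on Day 1 and the final visit on Day 379 (schedule of activities). Protocol 9.4 gives 16 participants inflated for 20% dropout, which reproduces: 16 / (1 − 0.20) = 20. Twenty per cent of 20 is 4.

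**Completers.** The last infusion is on Day 1 + 26 × 14 = 365. The tail to the final visit is 379 − 365 = 14 days, exactly one dosing interval. Nothing lies beyond one interval, so the missing end point has almost no effect.

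**Participants who leave the study.** Active AE collection ends with participation. After that, protocol 8.4.1 asks only for related SAEs that the investigator happens to learn of. The effect is about zero.

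**Participants who stop but stay in follow-up.** If infusion k is the last, its nominal day is d = 1 + (k − 1) × 14. Days beyond one dosing interval that still count as TEAE time are 379 − (d + 14). Total treatment-period person-time is 20 × (379 − 1) = 7,560 days. One interval serves here only as a yardstick.

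| Last infusion | Last dose day | Days beyond one interval | One stopper | Four stoppers |
|---|---|---|---|---|
| 4 | 43 | 322 | 322/7,560 = 4.3% | 1,288/7,560 = 17.0% |
| 8 | 99 | 266 | 266/7,560 = 3.5% | 1,064/7,560 = 14.1% |
| 14 | 183 | 182 | 182/7,560 = 2.4% | 728/7,560 = 9.6% |
| 20 | 267 | 98 | 98/7,560 = 1.3% | 392/7,560 = 5.2% |

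These shares assume that every stopper stays to Day 379 with AEs fully captured. They measure exposed time, not a number of events.

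**Could that time include Fabrazyme?** Protocol 6.8.1 prohibits only live vaccines, so nothing bars Fabrazyme during telephone follow-up. Protocol 6.8.2, the only place that mentions return to former treatment, couples it with leaving the trial. Protocol 7.1 lists Lyso-Gb3 changes judged to show lack of efficacy as a reason to stop the intervention while remaining in the study. The two sections do not agree on what follows from lack of efficacy and must be reconciled.

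**The case against.** **Return to Fabrazyme means leaving.** Protocol 6.8.2 ties the two together, and 7.2 ends study participation at that time. This stands: no section describes a participant back on Fabrazyme with AE collection continuing. It does not remove the point, because an AE recorded long after the last AGA BETA BS dose is counted under AGA BETA BS whether or not Fabrazyme has been resumed.

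**AE capture after stopping is thin.** Protocol Table 2 schedules AE and IAR assessment at intervention discontinuation and at the early discontinuation visit. Later calls cover general health and depend on the participant's agreement. This also stands, and it makes the percentages an upper illustration. Even so, a general-health call can bring an event to light, and 8.4.3 requires AEs already reported to be pursued at later contacts.

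**Four of 20 is the wrong group.** The 20% in protocol 9.4 is an allowance for early termination, and 7.2 uses the term dropouts for people who withdraw voluntarily, who leave the study. This stands; four is a ceiling for illustration and not a forecast of stoppers who remain.

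**Attribution is handled elsewhere.** SAP 17.1 also summarises AEs by relationship to each product. That helps the relatedness tables but not the all-causality AE, SAE and SOC/PT counts. SAP 17.1.1.1 and 17.1.1.2 also default a missing intensity to severe and a missing relationship to related, again with no end date.

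**The rule is conservative.** Counting everything after the first dose errs against the test product. That is a reason to keep the count as a supplementary table, but not as the only one.

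**Conclusion.** The TEAE definition lacks an upper limit in both SAP locations. Applied as written, it places recorded off-drug AEs in the all-causality AGA BETA BS tables. The problem is confined to participants who permanently stop AGA BETA BS and remain in follow-up under protocol 7.1. Its size is about zero for everyone else. For that group it is 1.3% to 17% of treatment-period person-time across the scenarios shown, if one to four stop, all stay to Day 379 and AEs are fully captured. How many will stop and stay cannot be known from the documents.

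A reader might infer more, but the documents do not support it:

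- *That events on Fabrazyme will be counted as AGA BETA BS events.* They may be, since nothing prohibits Fabrazyme during follow-up. But 6.8.2 links the return to leaving the trial, so this is a possibility and not a planned route.
- *That reactions to commercial Fabrazyme infusions will be counted as AGA BETA BS IARs.* SAP 17.1.5 defines an IAR by infusion of study drug. The yes/no field carries no product or date, but the definition points away from this reading.
- *That rates per infusion or per week are distorted.* SAP 14.1 does end exposure at the last dose while AE time runs on, but no exposure-adjusted AE rate is planned. AEs are reported as counts and percentages.

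**What to change.** In SAP 17.1 and Appendix 2:

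1. End the AGA BETA BS TEAE window at a stated interval after the last AGA BETA BS dose, or at the start of another ERT if that is earlier and known. The documents give no basis for a particular interval, so the sponsor should choose and justify it.
2. Summarise later events in a separate post-treatment class, mirroring the one already used for medications, and list them with the ERT being received where it is recorded.
3. Keep the count of all events after the first dose as a supplementary table.
4. In SAP 17.1.5, state that the IAR flag applies to study-drug infusions.

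Separately, reconcile protocol 6.8.2 and 7.1 on whether lack of efficacy leads to leaving the trial or to stopping the intervention with follow-up.

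The cost is some SAP wording, one derived flag and one extra table. Infusion dates and concomitant-medication dates are already recorded (protocol 6.4 and 6.8). One limit remains: start dates of another ERT may be incomplete, because protocol Table 2 schedules no medication review during telephone follow-up. Where the date is missing, the interval after the last dose would close the window.

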## 10.5 Appendix 5: AEs and SAEs: Definitions and Procedures for Recording, Evaluating, Follow-up, and Reporting for Study Intervention

### 10.5.1 Definition of Adverse Event

AE Definition

 
• An AE is any untoward medical occurrence in a clinical study participant administered a medicinal product and which does not necessarily have a causal relationship with that product.
 
• NOTE: An AE can therefore be any unfavorable and unintended sign (including an abnormal laboratory finding, for example), symptom, or disease (new or exacerbated) temporally associated with the use of study intervention/treatment, whether or not considered related to the study intervention/treatment.
 

Events Meeting the AE Definition

 
• Any abnormal laboratory test results (hematology, clinical chemistry, or urinalysis) or other safety assessments (eg, ECG, echocardiogram, vital signs measurements), including those that worsen from baseline, considered clinically significant in the medical and scientific judgment of the Investigator (ie, not related to progression of underlying disease).
 
• Exacerbation of a chronic or intermittent pre-existing condition including either an increase in frequency and/or intensity of the condition.
 
• New condition detected or diagnosed after study intervention administration even though it may have been present before the start of the study.
 
• Signs, symptoms, or the clinical sequelae of a suspected intervention-intervention interaction.
 
• Lack of efficacy or failure of expected pharmacological action per se will not be reported as an AE or SAE. Such instances will be captured in the efficacy assessments. However, the signs, symptoms, and/or clinical sequelae resulting from lack of efficacy will be reported as AE or SAE if they fulfill the definition of an AE or SAE.
 

Events NOT Meeting the AE Definition

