#### **Follow-up of AEs and SAEs**

- The Investigator is obligated to perform or arrange for the conduct of supplemental measurements and/or evaluations as medically indicated or as requested by the Sponsor or designee to elucidate the nature and/or causality of the AE or SAE as fully as possible. This may include additional laboratory tests or investigations, histopathological examinations, or consultation with other health care professionals.
- If a participant dies during participation in the study or during a recognized follow-up period, the Investigator will provide the Sponsor or designee with a copy of any postmortem findings including histopathology.
- New or updated information will be recorded in the originally submitted documents.
- The Investigator will submit any updated SAE data to the Sponsor or designee within 24 hours of the Investigator's awareness of the information.

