#### **17.1.2 AEs Leading to Discontinuation of Study Medication**

AEs leading to permanent discontinuation of patient will be identified by using Action taken as Discontinued in the CRF under Adverse Event.

AEs leading to discontinuation of patients from treatment will be listed with the reasons for discontinuation.

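### For adverse events with a known start date, treatment emergence is decided by onset alone, so a lead-in event that worsens after the switch can be left out of the AGA BETA BS tables if it stays on one record

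*SAP*

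**What the plan says.** SAP 17.1 ties treatment emergence to onset: AEs are TEAEs "if they start on or after the date of the first dose of AGA BETA BS", and these are tabulated for the Treatment period alone. All others are assigned, in a garbled phrase, as "Non-TEAEs under Lead-in period in treatment period". Appendix 2 turns this into an algorithm. For a known start date, whatever the stop date, it reads "If start date < study med start date, then not TEAE. If start date >= study med start date, then TEAE". The stop date matters only when the start date is missing, or is partial and could fall on or after the switch. SAP Appendix 1 labels the lead-in column Fabrazyme and the treatment column AGA BETA BS.

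SAP 17.1.1 gives an AE overview for both periods, including maximum severity and AEs leading to discontinuation. The tables by system organ class and preferred term, split by maximum severity and relationship, are for the Treatment period. So is the SAE summary in SAP 17.1.3. SAP 17.1.2 finds discontinuation events from one field: "AEs leading to permanent discontinuation of patient will be identified by using Action taken as Discontinued in the CRF under Adverse Event".

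On recording, the protocol points two ways. Section 10.5.1 counts as an AE "Exacerbation of a chronic or intermittent pre-existing condition including either an increase in frequency and/or intensity of the condition". Section 10.5.3 says of follow-up: "New or updated information will be recorded in the originally submitted documents". Section 10.3.9 leaves eCRF completion rules to a separate document.

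**The concern.** In a switch study of patients stable on the reference product, deterioration after the switch is one of the main things the safety tables should show. An onset-only rule is a weak instrument for that. A mild event that begins on Fabrazyme and turns severe or serious on AGA BETA BS keeps its lead-in start date if the site updates the existing record. It then sits in the reference column and drops out of the test product's severity, relationship and SAE tables.

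The default in SAP 17.1 that treats doubtful events as treatment-emergent does not help, because an event with a known lead-in start date is never doubtful. The descriptive counts also carry much of the weight here: Protocol 9.2.5 plans no formal safety analysis, and Protocol 10.3.7 states that there is no independent safety monitoring committee.

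**Working it through.** The plan gives no figure to reproduce, so the check applies the written rules to test cases.

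**Which events are exposed.** Protocol 8.4.1 records occurrences between consent and the start of study intervention as medical history, not as AEs. Protocol Table 4 lists Fabrazyme as a study intervention, and the Schedule of Activities puts its first infusion at Day -28 (±2). The exposed events are therefore AEs with onset from about Day -28 to Day -1 that are still open on Day 1. That is about four weeks, not the six weeks from the earliest screening day (Day -42). Protocol 8.4.3 follows AEs until they resolve or stabilise, so such an event can run past the switch.

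**Test cases.**

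| Case | Record | Result under SAP 17.1 and Appendix 2 |
|---|---|---|
| A | Onset Day -10, mild; severe on Day 15; one updated record | Not a TEAE. Lead-in/Fabrazyme. Absent from the Treatment-period AE tables, and from the SAE summary if it became serious |
| B | As A, but the worsening is entered as a new AE starting Day 15 | TEAE. AGA BETA BS, severe |
| C | Start date missing, or partial and possibly on or after Day 1; stop date on or after Day 1, or missing | TEAE. AGA BETA BS |
| D | Began between consent and first Fabrazyme infusion (medical history); exacerbation after the switch entered as an AE | Onset is post-switch, so TEAE |
| E | As A, and AGA BETA BS is stopped for it | The AE counts as leading to discontinuation in the Lead-in overview; the disposition table (SAP 9.1) still shows a Treatment-period discontinuation |

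In case A the SAP does not say which severity the lead-in overview shows. The overview item is maximum severity, so the event would appear as severe under Fabrazyme if the single record holds the worst grade.

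**Contrast with medications.** SAP 13 counts a drug started before the switch and ended on or after it as concomitant, and presents it under AGA BETA BS. In case A, a drug begun in the lead-in for the event and continued past the switch would be shown under AGA BETA BS while the event is shown under Fabrazyme.

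**Size per participant.** The planned number is up to 20 (SAP 3.1), and the required number before dropout is 16 (Protocol 9.4).

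- 1/20 = 0.050, or 5.0 percentage points
- 1/16 = 0.0625, or 6.25 percentage points

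This is the shift in one incidence for one affected participant. Neither document gives a rate for such events, so the total effect cannot be computed.

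**The case against.** The strongest reply is that a reader might infer more than the text supports: that post-switch worsening is always counted under Fabrazyme at its post-switch grade and never under AGA BETA BS. That needs one record overwritten with the worst grade, and no available section says so. Protocol 10.5.1 gives a route to a new AE on exacerbation, and it includes test results that worsen from baseline, which Protocol 9.2.1 sets at the last value before AGA BETA BS. The follow-up sentence in Protocol 10.5.3 stands among points on postmortem findings and 24-hour SAE updates; it sets no rule for onset date or severity. The eCRF guidance may already require a new record. All of this stands, and it makes the point conditional. It does not remove it: the exacerbation clause speaks of pre-existing conditions and need not cover an AE that arose in the lead-in, and nothing in the SAP stops the 5 sites from recording differently.

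A reader might also infer that stopping AGA BETA BS for such an event would be invisible on the AGA BETA BS side. It would not be. SAP 9.1 tabulates discontinuations by period with reasons, SAP 17.1.1 reports action taken for each drug by name, and the AE listings cover the ITT population. Only the AE-based discontinuation count is at risk.

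Nor does every rule favour the test product: missing or ambiguous start dates lean towards TEAE (case C). Worsening in laboratory values, ECG, echocardiogram and vital signs is also summarised by visit, whatever the AE coding. These points limit the damage but leave the gap for known start dates.

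**Conclusion.** The point holds in a conditional form. For a known start date, the SAP classes treatment emergence by onset alone and has no worsening clause, and the available documents do not settle how a severity increase across the switch is recorded. If it stays on one record, an AE with onset between about Day -28 and Day -1 that worsens or becomes serious after the switch is attributed to Fabrazyme and left out of the AGA BETA BS Treatment-period AE and SAE tables. Under that condition the shift runs only away from the test product.

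The size is 5.0 to 6.25 percentage points per affected participant, with unknown frequency. The conclusion assumes a known start date, a single record, and Fabrazyme read as study intervention for the medical-history cut-off. The stronger readings, that such events never count for AGA BETA BS or that a discontinuation would vanish from its results, are not supported. This is a definition worth correcting before database lock, not a flaw in the design.

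**What to change.** In SAP 17.1 and Appendix 2, define a TEAE as an AE that starts on or after the first AGA BETA BS dose, or that starts earlier and increases in severity or becomes serious on or after that dose. Then:

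- Use the date of worsening to assign the period. State whether a severity increase opens a new AE record, and align the eCRF completion guidance.
- Report the lead-in event at its pre-switch severity and the worsened event under AGA BETA BS.
- Place any AE whose action taken is discontinuation of AGA BETA BS under the Treatment period.
- While editing, repair the garbled non-TEAE phrase and the pointer to Appendix 1 for partial dates; the algorithm is in Appendix 2.

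The cost is SAP wording, one recording instruction, and a few extra AE records or queries. Some queries would be retrospective, since SAP 16.1 already reports 11 patients in the ITT population. AGA BETA BS counts may come out slightly higher.
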